### **5.3. Other Analysis Sets**

None.

### **5.4. Subgroups**

For the Xeljanz group, safety and efficacy will be analyzed for each of the following subgroups.

- Sex
- Age class ( $\geq 65$  years,  $< 65$  years)
- Presence or absence of hepatic dysfunction (Presence of hepatic dysfunction is defined as the item “current hepatic dysfunction” in the medical history being checked.)
- Presence or absence of renal dysfunction (Presence of renal dysfunction is defined as the item “current renal dysfunction” in the medical history being checked.)
- Average actual daily dose ( $< 7.5$  mg,  $\geq 7.5$  mg)

Patients that may be contraindicated in the package insert of Xeljanz (hereinafter referred to as contraindicated patients) are extracted based on the criteria specified separately, and a subpopulation analysis of safety is performed.

In addition, safety and efficacy will be analyzed for each of the patient background subgroups specified in Appendix 11.1.3 and 11.1.4.

## **6. ENDPOINTS AND COVARIATES**

### **6.1. Safety Endpoints**

#### **6.1.1. Comparison of Xeljanz group and control group**

- Malignant tumors are tumors with definitive diagnosis among all-causality malignant tumors (including lymphoma).
- Time to occurrence of malignant tumor
- Serious infections are infections corresponding to the following among all-causality infections.
  1. Results in death, or is life-threatening;

2. Results in disability, or may lead to disability;
  3. Requires inpatient hospitalization or prolongation of hospitalization;
  4. Are serious in accordance with the above.
- Time to occurrence of serious infection
  - Death refers to the case where the death column is checked in the status of treatment of Xeljanz (continued or discontinued) or the status of follow-up (continued or discontinued) in the case report form (CRF).

The death was defined to exclude post-survey deaths for comparing fairly in the Xeljanz and control groups, because post-survey deaths are likely to be collected only in the Xeljanz group. However, it was found that there were death cases that were possibly to have been confirmed at the end of the survey and had no reason for discontinuation of the treatment or the follow-up, when the final analysis for the reexamination application (cutoff data on 12/July/2021) was conducted. Since it was found that there were cases that were considered to be high, such cases were exceptionally regarded as cases where the investigation was discontinued due to patient death, and were included in the analysis as cases of death. Such cases were exceptionally regarded as death cases where the survey was discontinued due to death, and were included in the analysis as death cases. The handling of death cases is described in Section 7.

- Time to death

The causal relationship and seriousness of the adverse events (including malignant tumors, serious infections, and deaths) of the Xeljanz group in this survey were evaluated separately from the doctor's evaluation in the CRF and the corporate evaluation. In addition, after a patient in the Xeljanz group was transferred to a facility without a survey contract, the information obtained from the transfer destination is not described in the CRF, but there are adverse events entered in the database at the discretion of the company. Since this information is not collected in the control group, malignant tumors, serious infections, and deaths in the comparison between the Xeljanz group and the control group are investigated as adverse events including company evaluation and adverse events based only on the information described in the CRF.

#### **6.1.2. Safety analysis of the Xeljanz group**

- Adverse drug reactions (treatment-related adverse events).
- Adverse events (all-causality adverse events).

- Key survey items: The procedures to extract events to be handled as key survey items are specified in “Procedural Manual for Extracting Key Survey Items in Xeljanz Tablets 5 mg Special Investigation (All-Case).” Key survey items are shown below.

- *Serious infections;*
- *Neutrophil count decreased and neutropenia;*
- *Lymphocyte count decreased and lymphopenia;*
- *Hemoglobin decreased and anemia;*
- *Lipid increased and hyperlipidemia;*
- *Malignant tumors (including lymphoma);*
- *Gastrointestinal perforation;*
- *Cardiovascular adverse events;*
- *Hepatic dysfunction;*
- *Interstitial pneumonia.*

## 6.2. Efficacy Endpoints (Xeljanz Group)

- SDAI (Simplified Disease Activity Index)

$$\text{SDAI} = \text{TJC} + \text{SJC} + \text{PatientVAS [mm]} / 10 + \text{physician VAS [mm]} / 10 + \text{CRP [mg/dL]}$$

- CDAI (Clinical Disease Activity Index)

$$\text{CDAI} = \text{TJC} + \text{SJC} + \text{PatientVAS} \frac{[\text{mm}]}{10} + \text{physicianVAS [mm]} / 10$$

- DAS28 (4/ESR)

$$\text{DAS28(4/ESR)} = 0.56\sqrt{\text{TJC}} + 0.28\sqrt{\text{SJC}} + 0.70 \ln(\text{ESR [mm/hr]}) + 0.014(\text{Patient's VAS [mm]})$$

Unless otherwise specified, DAS28 (4/ESR) will be used as DAS28. If inconvenience occurs such as the case where there are many patients without the measurement of ESR and patient VAS, the use of DAS28 (3/ESR), DAS28 (4/CRP), or DAS28 (3/CRP) will be considered.

- DAS28 (3/ESR)

$$\text{DAS28(3/ESR)} = \{0.56\sqrt{\text{TJC}} + 0.28\sqrt{\text{SJC}} + 0.70 \ln(\text{ESR [mm/hr]})\} \times 1.08 + 0.16$$

- DAS28 (4/CRP)

$$\text{DAS28(4/CRP)} = 0.56\sqrt{\text{TJC}} + 0.28\sqrt{\text{SJC}} + 0.36 \ln(10 \times \text{CRP [mg/dL]} + 1) + 0.014(\text{PatientVAS [mm]}) + 0.96$$

- DAS28 (3/CRP)

### DAS28(3/CRP)

$$= \{0.56\sqrt{TJC} + 0.28\sqrt{SJC} + 0.36\ln(10 \times CRP[\text{mg/dL}] + 1)\} \times 1.10 + 1.15$$

TJC: Tender Joint Count

SJC: Swollen Joint Count

- Patient VAS and physician VAS

### 6.3. Covariates

For both the Xeljanz and control groups, candidate covariates related to the development of malignant tumors and serious infections are shown below.

Covariates	Malignant tumor	Serious infection
Sex	○	○
Age	○	○
Weight	○	○
Stage of rheumatoid arthritis	○	○
Class of rheumatoid arthritis	○	○
Duration or disease	○	○
Past history (infection)	×	○
Past history (malignant tumor)	○	×
Past history (lung disorder)	×	○
Past history (interstitial pneumonia)	×	○
Complication (infection)	×	○
Complication (malignant tumor)	○	×
Complication (hepatitis B)	○	×
Complication (hepatitis C)	○	×
Complication (diabetes mellitus)	×	○
Smoking history	○	○
Family history of malignant tumors (including lymphoma)	○	○
History of MTX use (Within 3 months prior to the start of survey)	○	○
MTX criteria	○	○
History of oral steroid use (Within 3 months prior to the start of survey)	○	○
History of tacrolimus use (Within 3 months prior to the start of survey)	○	○
Past use of biological agents (Within 3 months prior to the start of survey)	○	○

Covariats	Malignant tumor	Serious infection
Initial dose of Xeljanz	○	○
Neutrophil count	○	○
Lymphocyte count	○	○
Prophylactic administration to prevent tuberculosis	×	○
Prophylactic administration to prevent pneumocystis jiroveci pneumonia	×	○
Prophylactic administration to prevent hepatitis B	×	○
DAS28	○	○

○: Applicable, ×: Not applicable

Covariates may be added or removed based on the results of the interim analyses of this survey and newly obtained findings. In that case, this plan will be revised.

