## 7. HANDLING OF MISSING DATA

If there is no measurement within the acceptance range for the definition of visit timing for laboratory test values and efficacy endpoints (Appendix 11.1.1), data at the visit timing will be handled as missing.

If data on SDAI, CDAI, DAS28, TJC, SJC, patient VAS, physician VAS, ESR, or CRP is missing on Months 3 and 6, missing data will be imputed by LOCF using observed data after dosing for a sensitivity analysis on efficacy.

If the seriousness of, procedure for, and outcome of, adverse events are missing, they will be tabulated as "unknown."

If the date of event or death is missing for the analysis in consideration of time to the onset of malignant tumor and serious infection, and death, such a date will be imputed by the date on which no event or death is confirmed from among all data collected. The earliest of such date to complement the data would be the date on which the administration of Xeljanz or control drug therapy is started.

If the final date of dose or observation is missing, such a date will be complemented by the date on which a dose or observation is confirmed from among all data collected. The earliest of such date to complement the data would be the date on which the administration of Xeljanz or control drug therapy is started.

If candidate covariates (6.3) are missing (including unknown), they are not complemented in the univariate analysis. They are regarded as "unknown" and analyzed as one category in the multivariate analysis.

They are complemented by the multiple imputation method in the comparison of the Xeljanz group and the control group.

The death cases described in Section 6.1.1 define the cases in which treatment was not discontinued and continued until the end of the survey, or the cases in which no discontinuation was reported in the follow-up after discontinuation of treatment and death was reported within 3 years + 28 days from the start of treatment.

These are cases that meet the following two conditions and are regarded as cases in which the survey was discontinued due to death (the reason for discontinuation of the survey was death) in the comparison of deaths.

- Cases in which treatment has not been discontinued due to transfer or no return visit, and there is no reason for discontinuation of the survey.

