$$\times \sqrt{\frac{\sum \left( \frac{a_i N_{0i} - b_i N_{1i}}{S_i} \right)}{\sum \left( \frac{N_{1i} N_{0i}}{S_i} \right)} \sum U_i + \sum V_i}$$

$$U_i = \frac{N_{1i}^2 b_i - N_{0i}^2 a_i + N_{1i} N_{0i} (N_{0i} - N_{1i})/2}{S_i^2}$$

$$V_i = \frac{a_i (N_{0i} - b_i) + b_i (N_{1i} - a_i)}{2S_i}$$

- Adjusted hazard ratio and the 95% confidence interval

The hazard ratio adjusted for covariates and the 95% confidence interval will be estimated using a Cox proportional hazard model.

In addition, the proportional hazard assumption will be confirmed using the log-log plots of Kaplan-Meier estimates.

- **Propensity scores**

Propensity scores will be calculated by a logistic regression analysis and random forests using treatment groups as an objective variable and covariates described in “6.3 Covariates” as an explanatory variable. If candidate covariates (6.3) are missing (including unknown), they will be complemented by multiple imputation. The number of the datasets will be determined depending on a situation of the missing. This analysis is conducted by each dataset and the estimate is obtained by the integrated results

- **Analysis by multiple imputation method**

Missing data (including unknown) of covariates are complemented from variables with a small number of missing data by random forests using a fully conditional specification (FCS) algorithm as a multiple imputation method. The number of data sets to be complemented and created by the multiple imputation method is determined according to the rate of missing data. After complementation, analysis is performed for each created data set. The average value of the analysis results obtained for each data set is used as the point estimation value by the multiple imputation method. The point estimate and variance are calculated as follows.

$$\text{Point estimate } \bar{\theta}_M = \frac{1}{M} \sum_{m=1}^M \bar{\theta}_m$$

$$\text{Variance } T_M = \bar{W}_M + \left(1 + \frac{1}{M}\right) \bar{B}_M$$

$$\bar{W}_M = \frac{1}{M} \sum_{m=1}^M \text{var}(\bar{\theta}_m), \quad \bar{B}_M = \frac{1}{M-1} \sum_{m=1}^M (\bar{\theta}_m - \bar{\theta}_M)^2$$

- **Standardized incidence ratio (SIR) and the 95% confidence interval**

$$\text{SIR [%]} = \frac{\sum_{ij} d_{ij}}{\sum_{ij} p y_{ij} \lambda_{ij}} = \frac{D}{E}$$

Sex and age class	Reference population			Control population	
	Population	Number of patients	Incidence Rate	Duration of exposure	Number of patients

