### 8.2.3. Safety Analysis

#### 8.2.3.1. Comparison of Xeljanz group and control group

A comparison of the Xeljanz group and the control group is performed for each of the MTX adherent comparative analysis set and the comparative analysis set. The main analysis set is the MTX adherent comparative analysis set.

The adverse events including corporate evaluation is used for the main analysis, and as a secondary analysis, the analysis of adverse events based only on the doctor's evaluation is also used.

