**Table 5. Definitions in the Comparison of Malignant Tumors**

Term	Definition
Patients without malignant tumors	Patients who do not correspond to the each definition of patients with malignant tumors
Time to malignant tumor during overall observation period	Date of the development of malignant tumor - date of the initiation of treatment + 1
Censoring period for patients without malignant tumors during overall observation period	Date of completion or discontinuation of follow-up - date of the initiation of treatment + 1
Time to malignant tumor during treatment period	Date of the development of malignant tumor - date of the initiation of treatment + 1
Censoring period for patients without malignant tumors (treatment period)	Date of the completion of treatment - date of the initiation of treatment+ 1
Time to malignant tumor during the treatment period (+28 days)	Date of the development of malignant tumor - date of the initiation of treatment + 1
Censoring period for patients without malignant tumors during the treatment period (+28 days)	Date of the completion of treatment + 28- date of the initiation of treatment + 1

• **Development of malignant tumors**

The number of malignant tumors in each group and the proportion of occurrence are calculated for each SOC and PT. Furthermore, it is calculated for each cancer type (stomach, lung, breast, cervix, uterine body, ovary, malignant lymphoma, large intestine, pancreas, bladder, kidney / urinary tract (excluding bladder), other). Females are targeted for malignant tumors of the breast, cervix, uterine body and ovaries.

• **Incidence rate of malignant tumors**

The number of patients with malignant tumors in each group, incidence rate, and the 95% confidence interval will be calculated in accordance with [Section 8.1.5](#).

In addition, the incidence ratio between treatment groups and the 95% confidence interval and the difference in incidence rate between treatment groups and the 95% confidence interval will be calculated.

For covariates concerning malignant tumors (Section 6.3), incidence by single factor will be calculated, and the pooled incidence ratio and the 95% confidence interval and the pooled difference in incidence rate and the 95% confidence interval will be calculated.

• **Incidence proportion of malignant tumors**

The number of patients with malignant tumors in each group, the incidence proportion, and the 95% confidence interval will be calculated in accordance with [Section 8.1.5](#).

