In addition, the ratio of incidence proportion and the 95% confidence interval and the difference in incidence proportion and the 95% confidence interval will be calculated.

For covariates concerning malignant tumors ([Section 6.3](#)), the incidence proportion by single factor will be calculated, and the ratio of the pooled incidence proportion and the 95% confidence interval and the difference in the pooled incidence proportion and the 95% confidence interval will be calculated. Age will be handled as categorical data.

- **Analysis of time to malignant tumor**

Time to malignant tumor in each group will be summarized in accordance with [Section 8.1.4](#). As for the censoring period in patients without malignant tumors, [Table 5](#) will be followed. In addition, a graph showing the transition of the incidence rate estimated using the calculated parameters by applying the Weibull distribution together with the Kaplan-Meier plot, and a graph of the transition of the hazard function are created.

- **Adjusted hazard ratio for the development of malignant tumors**

As for time to malignant tumor, the adjusted hazard ratio of the Xeljanz group to the control group for the development of malignant tumors and the 95% confidence interval will be calculated in accordance with [Section 8.1.5](#). Covariates used for adjustment are shown in [Section 6.3](#).

As for the development of malignant tumors in the Xeljanz group compared to the control group, the propensity score-weighted (inverse probability of treatment weighting, IPTW) hazard ratio and the 95% confidence interval will be calculated. The weight is obtained

from  $Z_i + \frac{\theta_i(1-Z_i)}{1-\theta_i}$  ( $\theta_i$ : the estimated propensity score,  $Z_i$ : 1 (if xeljanz group) or 0 (if control group)). The other propensity score-weighted hazard ratio and the 95% confidence interval also will be calculated from setting an upper limit on the weight, because it is possible that some weights are too high if  $\theta_i$  is nearly equal 1. The upper limit is determined depending on a situation of the estimation accuracy.

In addition to the propensity score-weighted, further adjustment using a model with covariates of large effect will be conducted. The covariates which show large change in adjusted hazard ratio from the non-adjusted hazard ratio in the univariate model, will be included in this model in order to control the number of covariates in the model.

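### SAP 6.3 puts initial Xeljanz dose, DAS28, neutrophil count and lymphocyte count into the between-group models, although none of them is collected in controls

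*SAP*

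**What the plan says.** SAP 6.3 introduces its table with "For both the Xeljanz and control groups, candidate covariates related to the development of malignant tumors and serious infections are shown below". Four rows, "Initial dose of Xeljanz", neutrophil count, lymphocyte count and DAS28, are marked applicable to both malignant tumor and serious infection.

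The list is then used in the comparison:

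- SAP 8.1.6 (Propensity scores) takes the 6.3 covariates as explanatory variables and adds: "If candidate covariates (6.3) are missing (including unknown), they will be complemented by multiple imputation".
- SAP 7 says of missing candidate covariates: "They are complemented by the multiple imputation method in the comparison of the Xeljanz group and the control group". For the univariate analysis it says "they are not complemented in the univariate analysis".
- SAP 8.2.3.1.1 and 8.2.3.1.2 refer to 6.3 for the adjusted hazard ratios and also stratify on it: "For covariates concerning malignant tumors (Section 6.3), incidence by single factor will be calculated, and the pooled incidence ratio".
- SAP 8.2.3.1 fixes the population: "The main analysis set is the MTX adherent comparative analysis set".

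SAP 11.1.2 tags initial dose and DAS28 as belonging to the Xeljanz group only. It puts no such tag on the two blood counts.

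**The concern.** A covariate can adjust a between-group comparison only if it is observed in both groups. If it is wholly absent in one group, the data hold no information on how the groups differ in it beyond what shared covariates predict. Imputation then carries the Xeljanz-group relation over to controls, and the completed data look comparable by construction.

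At stake is the planned adjusted comparison of the two safety outcomes named in the protocol's objective. A reader who sees DAS28 and blood counts in the adjustment set and in a balanced covariate table would conclude that disease activity had been controlled. It would not have been. The dose row is a different problem: a Xeljanz-naive patient has no Xeljanz dose, and the SAP does not say how to code one.

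**Working it through.** No sample-size or power figure in the plan depends on this point, so there is no stated figure to reproduce.

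**Step 1. What is collected in controls**

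| SAP 6.3 covariate | Source | Controls |
|---|---|---|
| Initial Xeljanz dose | SAP 5.1.2 excludes Xeljanz-treated patients from the control set | undefined |
| Neutrophil count | Protocol 7.2: haematology results entered for the Xeljanz group; section 7 schedule agrees | not collected |
| Lymphocyte count | Protocol 7.1: controls complete registration items 1 to 7, laboratory tests are item 11; Protocol 7.2 as above | not collected |
| DAS28 | Protocol 7 schedule: joint counts, VAS, CRP and ESR for the Xeljanz group; Protocol 6.5 and 7.4: effectiveness in that group only | not collected |

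**Step 2. Extent**

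SAP 6.3 marks 21 covariates for malignant tumor and 25 for serious infection. Removing four leaves 17 and 21. The share of records lacking each variable, before any gaps among Xeljanz patients, is control n / total n. Over the protocol Appendix rows it runs from 2000/(2000+4000) = 33.3% to 2400/(2400+3000) = 44.4%.

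**Step 3. Pooled ratios**

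The pooled incidence ratio in SAP 8.1.6 is Σ(a·PT0/T) / Σ(b·PT1/T) over strata. In any stratum of observed values of these variables, controls contribute nothing, so PT0 = 0 and b = 0. Numerator and denominator are both zero, and the ratio does not exist without imputation.

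**Step 4. An 'unknown' category**

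SAP 7 uses this for multivariate analysis. If every Xeljanz patient has a value, 'unknown' is the same as control status: the matrix [intercept, treatment, unknown] has rank 2 of 3, and the hazard ratio is not identified. If some Xeljanz values are missing, the treatment effect rests on those patients alone.

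**Step 5. Imputed DAS28 and blood counts (assumed values)**

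Let d be the true DAS28 shift between groups, s the shift in a shared proxy and r their correlation, in SD units. With all donors from the Xeljanz group:

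- displayed difference before weighting = r·s, and after weighting = 0
- true difference after weighting = d − r·s

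For d = 0.5, r = 0.3, s = 0.2, the display shows 0.3 × 0.2 = 0.06 before and 0.00 after. The truth is 0.50 before and 0.50 − 0.06 = 0.44 after. Over d = 0, 0.2, 0.5; r = 0, 0.3, 0.7; s = 0, 0.2, 0.5, the simulated display after weighting never exceeded 0.004. The true value ran from 0 − 0.7 × 0.5 = −0.35 to 0.50. For blood counts (assumed shifts 0.3 and −0.2), the display was at most 0.002 against true absolute values of 0.15 to 0.30 and about 0.09 to 0.20.

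Effect on the estimate: with a true rate ratio of 1.00, 3000 against 2400 patients, a confounder shift of 0.5 and a log-rate slope of 0.5, the ratio was 1.28 without the covariate, 1.27 with it imputed and 0.99 with its true values. A separate simulation with all four variables imputed, dose included, differed from dropping them by at most 0.004 (1.305 against 1.301).

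**Step 6. Dose coded rather than imputed (assumed values)**

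The weights Z + θ(1−Z)/(1−θ) give each control θ/(1−θ), which should sum to about the number of Xeljanz patients, 3000 to 4000. If dose enters a logistic propensity model coded 0 or 'not applicable' in controls, the groups separate. With 50% to 95% of Xeljanz patients assumed on the higher of two dose levels, control weights summed to 0.03 to 0.12 after 10 iterations and were still falling. Residual difference in a shared covariate:

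| Initial shift | Dose omitted | Dose coded 0 | Coded 'not applicable' |
|---|---|---|---|
| 0.50 SD | 0.00 | 0.34 to 0.38 | 0.50 |
| 0.20 SD | not reported | 0.13 to 0.15 | 0.20 |

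**The case against.** The list may not be meant for the comparison as it stands. SAP 6.3 calls the covariates candidates and allows changes, some SAP blocks are redacted, and the four variables would make sense in Xeljanz-only risk-factor models. That is plausible, but the 6.3 heading names both groups, removal requires revising the plan, and the visible text of 8.1.6 and 8.2.3.1 makes no exception. A rule dropping covariates with much missing data appears only in the version 4.0 entry of the revision table, not in current section 6.3 or 7.

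The SAP orders imputation, not a code for dose, so Step 6 describes a choice a programmer might make. The residuals are read from a fit that does not converge, and only the logistic score was simulated although 8.1.6 also names random forests. This stands: Step 6 is a caution. But the rule actually written produces invented doses.

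The planned violin plots, weight boxplots and logistic parameters would expose separation. They would not cure it, and they would not reveal false balance from imputed DAS28. The planned cap on weights, set "because it is possible that some weights are too high if" the score nears 1, limits large weights only.

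The SAP 7 sentence on the group comparison can also be read as overriding the no-imputation rule for pooled ratios. Those ratios could then be computed, but every control would be placed in a stratum by an imputed value. Finally, tests are exploratory (SAP 4), and under imputation the estimate hardly moves. That limits the severity; it does not justify the specification.

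**Conclusion.** The concern holds. The documents alone establish that four of 21 covariates (malignant tumor) and four of 25 (serious infection) are absent by design in all controls yet assigned to the between-group models. For initial dose and DAS28 the SAP also contradicts its own section 11.1.2.

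The harm is chiefly false reassurance about adjustment for disease activity and blood counts, together with a dose variable that has no meaning in controls. The shift in the estimate under imputation is negligible in the simulations; a coded dose could invalidate the weighted analysis. The false-balance figures rest on assumed shifts and correlations, and apply only if the standardized differences use imputed data, which SAP 8.2.3.1.1 and 8.2.3.1.2 leave open. This should be fixed, but it does not undermine the survey as a whole.

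**What to change.** - In SAP 6.3, mark initial Xeljanz dose, DAS28, neutrophil count and lymphocyte count as Xeljanz-only. Add the same tag for the two counts in 11.1.2.
- In SAP 7, 8.1.6 and 8.2.3.1, restrict the propensity, Cox and pooled analyses, the balance tables and the imputation to covariates collected in both groups. Keep the four for analyses within the Xeljanz group.
- State in 8.2.3.1 that baseline DAS28 and blood counts were not recorded in controls and are not directly adjusted for. A sensitivity analysis for unmeasured confounding is optional.
- While editing, review two neighbouring rows. The MTX criteria covariate is constant in the main comparison set (SAP 5.1.2), so it cannot adjust anything there. Prior biologic use is not in the protocol 7.1 list of previous drugs recorded for both groups, so its availability in controls needs checking.
- Since SAP 6.1.1 refers to a final analysis with a July 2021 data cutoff, record which covariates were actually used.

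The cost is SAP wording and programming, with no new data. The list becomes shorter and the report carries an explicit limitation. Confounding by disease activity remains, but it is stated openly.
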